2.7.1.6 Time to at least a 10% increase from baseline in LVISD

An evaluation of the time from randomization to the first occurrence of an increase of at least 10% from the baseline value of LVISD (Left Ventricular Internal end-systolic dimension) will be performed based on the following variable:

• date of echocardiography assessment where a minimum of 10% increase first occurred minus date of randomization plus 1.

The time-to-event analysis follows the description given in Section 2.5.2.2. Censoring for patients without such an increase in LVISD will be at the time of a last LVISD assessment (Section 2.7.3.3).

2.7.1.7 Time to first occurrence of serum ferritin > 2 times the baseline value

An evaluation of the time from randomization to the first occurrence of serum ferritin > 2 times the baseline value at two consecutive assessments (at least two weeks apart) will be performed per treatment group based on the following variable:

date of the first of the two consecutive laboratory assessment fulfilling the criterion of SF > 2
 × baseline value minus date of randomization plus 1

The time-to-event analysis follows the description given in Section 2.5.2.2. Censoring for patients without such a serum ferritin increase is described in Section 2.5.3.6.

2.7.1.8 Infections

Infections requiring intravenous antimicrobials during the treatment period (until the 28 day follow-up visit) will be evaluated separately for each treatment group.

Definitions:

- Infections will be determined from the reported adverse events with system organ class "Infections and infestations" and action taken "Concomitant medication taken".
- Antimicrobial therapy will be determined from the reported concomitant medications for patients who had an infection AE. The medications will be based on a pre-specified list of WHO low level ATC codes. The route of administration needs to be specified as "intravenous (i.v.)".
- Identified events will be combined with medications (of the same patient) based on the following criterion: start date of medication ≥ start date of AE and start date of medication ≤ minimum (start date of AE + 1, end date of AE).

The total number of infections requiring intravenous antimicrobials will be counted and summarized per treatment group. For this number, one patient can contribute more than one infection event. To account for different lengths of observation time in the two groups, the rate of infections will be calculated with the number of recorded infections treated with intravenous antimicrobials divided by the total number of patient-years of follow-up. The relative risk of infection will be calculated as the rate of infection in the treatment group compared with the rate in the placebo group.

2.7.2 Statistical hypothesis, model, and method of analysis

No hypothesis will be tested for secondary endpoints.

2.7.3 Handling of missing values/censoring/discontinuations

2.7.3.1 Overall survival

For the analysis of overall survival (see Section 2.7.1.1), patients will be censored at the last contact date.

2.7.3.2 Disease progression to MDS

For the analysis of time to disease progression (see Section 2.7.1.4), patients who did not experience an MDS progression will be censored at the last contact date.

2.7.3.3 Increase in LVIDD or LVISD

For the two analyses of time from randomization to the first occurrence of an increase of at least 10% from the baseline value of LVIDD and time from randomization to the first occurrence of an increase of at least 10% from the baseline value of LVISD (see Section 2.7.1.5 & 2.7.1.6), respectively, patients who did not experience such an increase will be censored at the last date when LVIDD (or LVISD, respectively) was available.

2.8 Safety analyses

As stated in the protocol (Section 3.2), one of the secondary objectives was to evaluate safety, in particular to assess the levels of increased risk for pre-specified adverse events (renal dysfunction, neutropenia, thrombocytopenia, gastrointestinal bleeding, and laboratory abnormalities) that would be clinically unacceptable in the context of the level of benefit that is likely to be provided by iron chelation using deferasirox in MDS patients with iron overload.

Endpoints for the secondary safety objectives are as follows:

- 1. Proportion of patients with significant renal dysfunction
- 2. Proportion of patients with newly occurring moderate or severe neutropenia or thrombocytopenia
- 3. Proportion of patients with major gastrointestinal bleeding
- 4. Time to study drug discontinuation due to an adverse event or laboratory abnormality
- 5. Incidence of other adverse events and laboratory abnormalities

The first four endpoints are defined and evaluated as follows:

Proportion of patients with significant renal dysfunction defined as serum creatinine ≥ 2 times ULN at two consecutive assessments (at least 7 days apart) Frequency tables by treatment group will be prepared along with a two-sided 95% confidence interval for evaluation of DFX in contrast to placebo. Results will also be

Endpoint	Analysis
Proportion of patients with newly occurring neutropenia (absolute neutrophils count <1.0×10 ⁹ /L) or thrombocytopenia (platelets <50×10 ⁹ /L)	provided for annual time intervals.
Proportion of patients with major gastrointestinal bleeding.	
Time to study drug discontinuation due to an AE or laboratory abnormality, more specifically date of study drug discontinuation due to an AE or laboratory abnormality minus date of randomization plus 1.	The time-to-event analysis follows the description given in Section 2.5.2.2 The statistical test will be exploratory in nature. For the analysis of time from randomization to study drug discontinuation due to an AE or laboratory abnormality (see Section 2.8.3), patients who did not discontinue study medication due to an AE or laboratory abnormality will be censored at the date of study drug discontinuation.

Proportion of patients with moderate or severe anemia will be analyzed like newly occurring neutropenia.

Other analyses and other safety data (ocular and auditory examinations, electrocardiogram, and vital signs) will be also considered.

Safety summary includes baseline and on-treatment period. All safety data (including those from the post-treatment period) will be listed and those collected during the pre-treatment and post-treatment periods will be flagged.

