For each treatment group, survival functions for time from randomization to the composite primary endpoint (event-free survival) will be estimated and displayed by the Kaplan-Meier method.

Sensitivity/supportive/exploratory analyses for the primary endpoint:

- Point estimate and two-sided confidence interval for an adjusted hazard ratio from a Cox proportional hazard regression model stratified for the randomization factors; adjustment for (partly data driven) demographic and/or baseline characteristics of clinical interest:
- Unadjusted hazard ratio estimates for each of the strata defined by the randomization factors;
- Analysis analog to the primary statistical analysis but patients with premature discontinuation of randomized study treatment will be censored at the day of last administration of randomized study treatment;
- Summary of the types of events observed;
- Statistical analyses based on the PPS instead of the FAS.

Statistical analysis methods for secondary efficacy endpoints:

Analyses will be described in the full clinical study protocol.

Statistical analysis methods for safety endpoints:

Following (Fleming 2008), the goal of this exploratory trial is not to determine whether there is significant evidence to rule out the null hypothesis of no increased risk.

In contrast, the objective here is to exclude levels of increased risk (for pre-specified adverse events mentioned in the Endpoints section) that would be clinically unacceptable in the context of the level of benefit that is likely to be provided by iron chelation using deferasirox in MDS patients with iron overload. Therefore, two-sided 95% confidence intervals for risk (or hazard, if applicable) ratios will be calculated. Incidences of treatment emergent (serious) adverse events (including combinations of MedDRA terms as defined by Standardized MedDRA Queries) will be summarized by treatment group. Laboratory data will be summarized using descriptive statistics and shift tables (using CTCAE classification where available) by treatment group.

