### 10.5.2.2 Secondary safety variables and related analyses

Analyses of safety endpoints related to secondary objectives of the trial will be analyzed for the safety analysis set. Descriptive statistics and two-sided 95% confidence intervals (without adjustment for multiplicity) for evaluation of deferasirox in contrast to placebo will be used as appropriate.

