2.1.1 General presentation of descriptive summaries

Qualitative data (e.g., gender, race, etc.) will be summarized by frequency count and percentages. Percentages will be calculated using the number of patients in the relevant population or subgroup as the denominator.

Quantitative data (e.g., age, body weight, etc.) will be summarized by appropriate descriptive statistics (e.g., mean, standard deviation, median, minimum, and maximum).

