2.1.2.9 On-treatment assessment/event and observation periods

The overall observation period will be divided into three mutually exclusive segments:

- 1. *pre-treatment period*: before the first administration of study treatment
- 2. *on-treatment period*: from date of first administration of study treatment to 28 days after date of last actual administration of any study treatment (including start and stop date)
- 3. *post-treatment period*: starts on day 28+1 after last administration of study treatment.

Per study design, there will be two additional observation periods:

- 4. *study evaluation period:* starts on day 29 after last administration of study treatment until study evaluation completion period (visit frequency every three months)
- 5. **survival follow-up period:** starts after study evaluation completion visit until LPFV plus three years or death. If a patient declines to participate in the evaluation period, the survival follow-up period will start on day 29 after last administration of study treatment until LPFV plus three years or death (visit frequency is every 6 months).

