5.5.3 Confidence interval for the difference of proportions

The 95% confidence limits for the difference of two proportions will be derived as the Wilson score confidence limits, i.e. in Proc Freq riskdiff-option: CL=WILSON(CORRECT).

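### SAP 2.8 leaves the scale of the safety confidence interval unnamed for three pre-specified risks, allows for unequal time at risk only through annual tables without a stated denominator, and omits the recurrent GI-bleeding analysis

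*SAP*

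**What the plan says.** The safety objective, in the protocol synopsis and repeated in SAP 2.8, concerns increases in risk that would be clinically unacceptable given the likely benefit. The synopsis says how: "two-sided 95% confidence intervals for risk (or hazard, if applicable) ratios will be calculated". Protocol 10.5.2.2 is looser: "Descriptive statistics and two-sided 95% confidence intervals (without adjustment for multiplicity) for evaluation of deferasirox in contrast to placebo will be used as appropriate".

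For the three proportion endpoints (significant renal dysfunction, newly occurring neutropenia or thrombocytopenia, major GI bleeding), SAP 2.8 states: "Frequency tables by treatment group will be prepared along with a two-sided 95% confidence interval for evaluation of DFX in contrast to placebo". It adds results by annual interval. Four other SAP rules bear on this:

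- Denominators (SAP 2.1.1): "Percentages will be calculated using the number of patients in the relevant population or subgroup as the denominator".
- Data included (SAP 2.8): "Safety summary includes baseline and on-treatment period".
- The on-treatment period (SAP 2.1.2.9) runs "from date of first administration of study treatment to 28 days after date of last actual administration".
- The only two-group interval method given for proportions (SAP 5.5.3): "The 95% confidence limits for the difference of two proportions will be derived as the Wilson score confidence limits". It is cited from hematologic improvement in SAP 2.7.1.1, not from SAP 2.8.

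For infections, over essentially the same window, SAP 2.7.1.8 divides by patient-years, with the reason "To account for different lengths of observation time in the two groups".

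Protocol 10.5.2.2 also commits to a recurrent-event analysis of major GI bleeding. SAP 2.8 has none, and SAP section 4 lists a single change from the protocol: the redefinition of the cytopenia endpoint.

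**The concern.** Three gaps meet here.

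**Scale.** A programmer working from SAP 2.8 cannot tell whether the interval is for a risk ratio, a difference or something else. The synopsis specifies a ratio; the SAP does not carry it forward.

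**Time at risk.** Observation ends when the patient's own treatment ends, plus 28 days. Treatment length is open-ended: the exposure bands in SAP 2.4 run from under 379 to at least 1835 days. Several rules could make stopping differ by arm: discontinuation at a confirmed non-fatal primary event (Protocol section 4), the creatinine rules (Protocol 6.7.1.3), and switching to other chelation, for which SAP 5.5.4 plans if placebo exceeds deferasirox by more than 10%. If one arm is observed for less time, a crude proportion mixes drug effect with exposure. For an objective about excluding excess harm, that can hide a risk or create one.

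**Undeclared omission.** The recurrent GI-bleeding analysis has disappeared without record. This rests on the text alone.

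**Working it through.** The documents give no event rate, margin or expected exposure for these endpoints, so there is no figure of the plan's to reproduce. The check is an illustration.

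**Inputs from the documents:** 210 patients at 2:1, so 140 deferasirox and 70 placebo; window ending at last dose + 28 days (0.0767 yr); last scheduled treatment week 372, so a cap of 372 × 7 = 2604 days (7.129 yr).

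**Assumed inputs:** exponential time on treatment T with mean m; placebo hazard 0.05, 0.1 or 0.2 per year; true hazard ratio (HR) 1.5 or 1.0; mean treatment 1.0, 1.35 or 1.5 yr.

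**Formulas.** Window W = min(T, cap) + d. With hazard h(s) and event-free survival S(s), P(event) = ∫ h·S·P(W>s) ds and patient-years at risk = ∫ S·P(W>s) ds. For constant hazard λ and μ = 1/m:

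P = 1 − e^(−λd) + e^(−λd) · λ/(λ+μ) · (1 − e^(−(λ+μ)·cap))

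**Worked case, placebo hazard 0.1, HR 1.5:**

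- Placebo, m = 1.5: 0.0076 + 0.9924 × 0.1304 × 0.9958 = 0.1365.
- Deferasirox, m = 1.0: 0.0114 + 0.9886 × 0.1304 × 0.9997 = 0.1403. Crude ratio 0.1403/0.1365 = 1.03.
- Deferasirox, m = 1.5 (equal exposure): 0.0114 + 0.9886 × 0.1837 × 0.9970 = 0.1925. Crude ratio 0.1925/0.1365 = 1.41.

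The fair comparator is the equal-exposure ratio, not 1.5, because a risk ratio lies nearer 1 than the hazard ratio when events are not rare.

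**Crude ratio over placebo hazards 0.05–0.2:**

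| Mean treatment, deferasirox vs placebo | True HR 1.5 | True HR 1.0 |
|---|---|---|
| 1.5 vs 1.5 yr | 1.35–1.45 | 1.00 |
| 1.35 vs 1.5 yr (10% gap) | 1.26–1.33 | – |
| 1.0 vs 1.5 yr | 1.03 | 0.70–0.74 |
| 1.5 vs 1.0 yr | 1.82–2.06 | 1.35–1.42 |

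**Annual tables, 1.0 vs 1.5 yr.** In year 1 every treated patient is at risk at the start, so the denominator is not in doubt. The year-1 ratio is 1.28–1.32 at HR 1.5, against 1.44–1.48 at equal exposure, and 0.89 under no effect. In year 2 the denominator matters: at HR 1.5 the ratio is 0.83–0.92 over all treated patients and 1.26–1.29 over those still at risk.

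**Which adjusted measure.** With constant hazard the patient-year rate ratio and the hazard ratio both return the true value. With a front-loaded hazard (0.3 per year for 6 months, then 0.03), 1.0 vs 1.5 yr:

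- No effect: crude 0.88, rate ratio 1.26, hazard ratio 1.00.
- True HR 1.5: crude 1.27 (1.43 at equal exposure), rate ratio 1.93, hazard ratio 1.50.

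With a rising hazard (0.03 in year 1, then 0.2) and no effect: crude 0.59, rate ratio 0.81, hazard ratio 1.00. The hazard ratio is recovered because proportional hazards and uninformative stopping are assumed. If 20% of deferasirox events never appear because toxicity stops the drug first, a true 1.5 becomes about 1.5 × 0.8 = 1.20.

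**Precision**, hazard 0.1, HR 1.5, 1.0 vs 1.5 yr, about 20 vs 10 events: crude 1.03 (95% CI 0.50–2.11); hazard or rate ratio 1.50 (about 0.69–3.25).

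**The case against.** The strongest reply is that most of this is already covered. The protocol defines these endpoints as proportions, and a crude risk ratio would satisfy the synopsis. The annual split partly stratifies by time, and year 1 removes much of the distortion. SAP 2.4 reports exposure and total patient-years by arm, so an imbalance would be visible. Discontinuation for an adverse event or laboratory abnormality has its own time-to-event analysis. Protocol 6.7.2 requires weekly follow-up for four weeks after stopping for an abnormal laboratory value, so a confirming creatinine can still fall inside the window. Adjusted measures have biases too, and the intervals overlap heavily.

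Much of that stands. It rules out saying that the SAP relies on crude proportions alone, and it makes exposure adjustment an addition rather than a correction. It does not answer three things: the scale is unnamed; showing patient-years lets a reader see an imbalance but does not adjust the comparison; and the GI-bleeding analysis is missing without declaration. The infections parallel is only partial, since that endpoint is defined as a rate and counts repeat events.

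A reader might also infer that the safety interval is for a difference, because SAP 5.5.3 gives nothing else. The documents do not support that: SAP 2.8 does not cite 5.5.3, so a ratio is unspecified rather than excluded.

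**Conclusion.** The point holds as a specification gap with a conditional bias. SAP 2.8 does not carry forward the synopsis's ratio scale, and beyond an annual split with no stated at-risk denominator it makes no allowance for unequal time at risk. With a one-third shorter mean treatment on deferasirox, a true hazard ratio of 1.5 would show as a crude 1.03 where equal exposure gives 1.35–1.45; with the imbalance reversed it would show as 1.82–2.06. A 10% gap shifts the ratio only to 1.26–1.33.

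All exposures and hazards behind these figures are assumed. It would be tempting to conclude that the plan will hide harm. The documents do not show that exposure differs by arm, or in which direction, so that does not follow. With no stated margin, wide intervals and an exploratory purpose, no formal decision changes: the exposure-adjusted part is a modest, cheap improvement. The missing recurrent GI-bleeding analysis is a plain inconsistency and needs no assumptions.

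**What to change.** 1. State in SAP 2.8 that the 95% interval accompanying the crude proportions is for the risk ratio, as the synopsis provides, and name the method.
2. Add one supportive on-treatment time-to-first-event analysis per endpoint, from first dose to first event or last dose + 28 days, with hazard ratio and 95% interval, which the synopsis allows. Date confirmed events at the initial instance. State the time origin explicitly, because Protocol section 10 counts from randomization. Give patient-year rates as description only, since their ratio misleads when the hazard is not constant.
3. Use patients still at risk at the start of each year as the annual denominator.
4. Restore the recurrent GI-bleeding analysis in SAP 2.8, or list its removal in SAP section 4.
5. Say in the report that toxicity-triggered stopping may still bias the hazard ratio. This matters most for the renal endpoint, where the discontinuation threshold in Protocol 6.7.1.3 lies close to the endpoint threshold.

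The cost is SAP wording, a derived time-at-risk variable for each endpoint (the patient-years in SAP 2.4 are total exposure) and a few tables. No new data are needed. The drawback is that the estimates may disagree, which is why the hazard ratio should be labelled supportive in advance.

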2.8.1 Adverse events (AEs)

All AEs recorded during the study are coded using the latest version of the medical dictionary for regulatory activities (MedDRA) and summarized by treatment group and overall. Adverse events are not assessed according to the common terminology criteria for AEs (CTCAE); instead, AE severity (mild, moderate, severe) is used to report treatment-emergent AEs starting on or after the date of first study medication (including AEs that start within 28 days after the discontinuation of the study medication).

Frequency tables for treatment-emergent AEs will be presented, for each treatment group, the number of patients, and the percentage of patients experiencing the AE. Multiple occurrences of the same event in the same patient will be counted only once in the frequency tables. However, all adverse events will be included in the AE listings.

Frequency tables will display at least the MedDRA system organ class and preferred term, AE severity (mild, moderate, severe), and relationship to study drug. The following tables will be generated:

• Adverse events, regardless of study drug relationship

- Serious adverse events, regardless of study drug relationship
- Serious adverse events, suspected to be study drug relationship
- Adverse events leading to study drug discontinuation, regardless of study drug relationship
- Adverse events requiring dose adjustment or interruption, regardless of study drug relationship
- Adverse events requiring additional therapy, regardless of study drug relationship
- Adverse events, suspected to be study drug related
- Adverse events which are not serious adverse events, regardless of study drug relationship

For the requirements of ClinicalTrials.gov and EudraCT, two required tables on <ontreatment/treatment emergent> adverse events which are not serious adverse events with an incidence greater than 5% and on <on-treatment/treatment emergent> serious adverse events and SAE suspected to be related to study treatment will be provided by system organ class and preferred term on the safety set population.

If for a same patient, several consecutive AEs (irrespective of study treatment causality, seriousness and severity) occurred with the same SOC and PT:

- a single occurrence will be counted if there is ≤ 1 day gap between the end date of the preceding AE and the start date of the consecutive AE
- more than one occurrence will be counted if there is > 1 day gap between the end date of the preceding AE and the start date of the consecutive AE

For occurrence, the presence of at least one SAE/SAE suspected to be related to study treatment / non SAE has to be checked in a block e.g., among AE's in a \leq 1 day gap block, if at least one SAE is occurring, then one occurrence is calculated for that SAE.

The number of deaths resulting from SAEs suspected to be related to study treatment will be tabulated by SOC and PT and a listing will be generated.

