## 7.5.1 Adverse events

An adverse event for the purposes of this protocol is the appearance of (or worsening of any pre-existing) undesirable sign(s), symptom(s), or medical condition(s) occurring after signing the informed consent even if the event is not considered to be related to the study drug(s). However, it must be noted that MDS is not considered an adverse event. MDS is a required condition for study entry and is expected to be reported as Medical History for all patients. Time to disease progression is a secondary efficacy endpoint. Please refer to Section 6.1 for the protocol-specific definitions of study drug and study treatment.

Adverse events (but not serious adverse events) occurring before starting study treatment but after signing the informed consent form are recorded on the Medical History/Current Medical Conditions eCRF. Abnormal laboratory values or test results that induce clinical signs or symptoms, are considered clinically significant, require therapy (e.g., any hematological abnormality that requires transfusion or cytokine treatment), or interruption of study medication should be recorded on the Adverse Events eCRF under the signs, symptoms or diagnosis associated with them. Abnormal Laboratory values that do not meet this criteria are not reported as Adverse Events. SAEs occurring after signing the Informed Consent are recorded on the Adverse Event eCRF.

The occurrence of adverse events should be sought by non-directive questioning of the patient at each visit during the study. Adverse events also may be detected when they are volunteered by the patient during or between visits or through physical examination, laboratory test, or other assessments. As far as possible, each adverse event should be evaluated to determine:

- 1. The severity grade (mild, moderate, severe)
- 2. Its relationship to deferasirox (suspected/not suspected)

- 3. Its duration (start and end dates or if continuing at final examination)
- 4. Action taken (no action taken; study drug dosage adjusted/temporarily interrupted; study drug permanently discontinued due to this adverse event; concomitant medication taken; non-drug therapy given; hospitalization/prolonged hospitalization)
- 5. Whether it is serious, where a serious adverse event (SAE) is defined as one which:
  - Is fatal or life-threatening
  - Results in persistent or significant disability/incapacity
  - Constitutes a congenital anomaly/birth defect

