## 10.5.2 Secondary safety objectives

#### 10.5.2.1 Observation periods for safety

The overall observation period will be divided into three mutually exclusive segments:

- 1. Pre-treatment period: from day of patient's informed consent to the day before first dose of study medication.
- 2. On-treatment period: from day of first dose of study medication to 28 days after last dose of study medication.
- 3. Post-treatment period: starting at day 29 after last dose of study medication.

Safety summaries (tables and figures) have to include only data from the pre-treatment period (to display "baseline status") and the on-treatment period, i.e. no data from the post-treatment period are to be included. In particular, summary tables for adverse events (AEs) will include only AEs that occurred or worsened during the on-treatment period, the so-called **treatment-emergent** AEs.

However, all safety data (including those from the post-treatment period) will be listed and those collected during the pre-treatment and post-treatment periods will be flagged.

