Clinical Development

ICL670/Deferasirox/Exjade®

Study Number: CICL670A2302 / NCT00940602

A multi-center, randomized, double-blind, placebo-controlled clinical trial of deferasirox in patients with myelodysplastic syndromes (low/int-1 risk) and transfusional iron overload (TELESTO)

RAP Module 3- Detailed Statistical Methodology

Author:	Trial Statistician

Document type: RAP Documentation

Document status: Amendment 4

Release date: 19-Apr-2018

Number of pages: 46

Property of Novartis
For business use only
May not be used, divulged, published or otherwise disclosed
without the consent of Novartis

Date	Version	Outcome/changes
11Mar2015	Final	• RAP M3
04Apr2017	Amend ment 1	• The previous final RAP was lean and did not include standard sections. Examples include, study design, definitions of baseline, etc. The amendment is an adaptation of the new SAP template. Section numbers listed in the current RAP amendment follow the current M3 template.
		• Per new template, added study design (Section 1.1)
		• Tabulated study objectives and endpoints (Section 1.2)
		 Added a few definitions including last contact date (Section 2.1.2.4)
		• Clarified baseline definition (Section 2.1.2.8)
		 Added two observational periods: study evaluation period and survival follow-up period (Section 2.1.2.9)
		• Elaborated and added the criteria for Per Protocol Set (PPS) associated with severity code 1 (Section 2.2.2)
		• Deleted randomized population set (Section 2.2.3)
		• Modified the language for disposition table (Section 2.3)
		 Added analysis language for relevant medical history and current medical condition and also for hemoglobin history (Section 2.3)
		• Included time-intervals for duration of exposure categories (Section 2.4)
		• Clarified primary endpoint definition (Section 2.5.1)
		• Clarified that statistical significance level is indeed 2.5% in a one sided test (Section 2.5.2.1)
		• Clarified HI (Hematologic Improvement) definition (Section 2.7.1.1)
		• Elaborated time-to event analysis in terms of what will be displayed (Section 2.7.1.1)
		• Added the definition of treatment emergent AEs and also list of AE tables (Section 2.8.1)
		• Included two AE tables for the requirement of ClinicalTrials.gov and EudraCT: Non-serious adverse

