2.13 Interim analysis

No interim analysis will be performed.

3 Sample size calculation

The sample size of 210 patients randomized in a ratio of 2:1 in favor of deferasirox is based on the feasibility of enrolling the patients and consultations with the Health Authorities. As noted earlier, this study is not powered for any confirmatory primary or secondary endpoints.

4 Change to protocol specified analyses

The following change was made:

• Newly occurring thrombocytopenia and neutropenia was redefined using the definition of the corresponding notable laboratory abnormalities

5 Appendix

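### SAP 2.8.1 defines treatment-emergent AEs by start date alone and, without declaring it, drops the protocol's criterion for AEs that worsen on treatment

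*SAP*

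**What the plan says.** Protocol 10.5.2.1 sets the on-treatment period as the day of first dose to 28 days after the last dose. It then says that "summary tables for adverse events (AEs) will include only AEs that occurred or worsened during the on-treatment period", and it calls these events treatment-emergent.

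SAP 2.8.1 keeps that window but describes the reported events as "treatment-emergent AEs starting on or after the date of first study medication". A parenthesis then carries the rule past the end of dosing: "including AEs that start within 28 days after the discontinuation of the study medication". Both ends are set by the start of the event. The SAP's change log for its Amendment 1 records: "Added the definition of treatment emergent AEs and also list of AE tables". So this is the working definition and not a passing phrase.

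SAP Section 4, on changes to protocol-specified analyses, says "The following change was made" and gives one entry: "Newly occurring thrombocytopenia and neutropenia was redefined using the definition of the corresponding notable laboratory abnormalities". The treatment-emergent definition does not appear there.

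Three recording rules decide who is affected:

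- Protocol 7.5.1 treats the worsening of a pre-existing condition as an AE in its own right.
- The same section sends non-serious events between consent and first dose to the Medical History page, whereas "SAEs occurring after signing the Informed Consent are recorded on the Adverse Event eCRF".
- Protocol 8.1 has progression of an SAE reported as follow-up of the first episode, not as a separate event.

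**The concern.** The protocol has two routes into the AE tables: starting on treatment and worsening on treatment. The SAP has only the first. An event that was open at the first dose and deteriorated afterwards can enter only by the second route, so the SAP rule removes it.

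One of the trial's stated safety objectives is to judge whether any increase in risk is clinically unacceptable. For that purpose an undercount is the unhelpful direction of error. The change is also silent: someone who checks Section 4 for departures from the protocol would not find it, and the tables would look as if they followed the protocol.

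**Working it through.** No sample size, power or event count is at issue. The check sets the two definitions side by side and follows each kind of record through them.

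**Step 1. Does anything else in the SAP restore worsening?** No. SAP 2.1.2.9 and the closing text of SAP 2.8 give only the observation periods. The partial-date rules in SAP 5.1.2 place an AE by its start date relative to treatment start.

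**Step 2. How do the two sets relate?**

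- Protocol set = {starts on treatment} ∪ {worsens on treatment}.
- SAP set = {starts on treatment}.
- The SAP set is contained in the protocol set, so a count can fall but cannot rise.

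**Step 3. Which records fall in the difference?**

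| Event | Where recorded | Protocol 10.5.2.1 | SAP 2.8.1 |
|---|---|---|---|
| New event after first dose | AE page | counted | counted |
| Non-serious event or chronic condition before first dose, worsens on drug | Medical History; the worsening is itself an AE | counted | counted, if the new record is dated at the worsening |
| SAE between consent and first dose, worsens on drug, record keeps its original start date | AE page | counted | **not counted** |
| The same SAE, worsening entered as a new record dated on treatment | AE page | counted | counted |

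The third row is the gap. It can arise because pre-dose SAEs go on the AE page and because SAE progression is reported as follow-up of the first episode. Protocol 7.5.1 also has an AE followed to resolution with severity changes assessed at each visit, which is compatible with updating a single record.

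**Step 4. Which outputs use the rule?** The treatment-emergent frequency tables in SAP 2.8.1: all AEs, SAEs, drug-related events, events leading to discontinuation, and events requiring dose adjustment or interruption. The groupings of special interest and the AE-based gastrointestinal bleeding endpoint would follow only if they apply the same rule, which the SAP does not state.

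The following do not use it:

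- the death summaries (SAP 2.8.2);
- time to discontinuation, taken from the treatment completion page (Protocol 10.5.2.2);
- the laboratory-defined renal and cytopenia endpoints (SAP 2.8);
- the laboratory shift and notable-value tables (SAP 2.8.3);
- the listings, which hold all AEs.

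**Step 5. Scale per patient.** The documents give no number of screening SAEs, so no total can be computed. With the planned 210 patients at 2:1, the arms are 210 × 2/3 = 140 and 210 × 1/3 = 70. One patient lost from a table row lowers that row by 1/140 = 0.7 percentage points on deferasirox or 1/70 = 1.4 points on placebo. This is a unit of scale, not an estimate of how many are lost.

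**The case against.** The strongest reply is that almost nothing falls through. The patient must have an SAE between consent and first dose, in a screening period planned at up to 35 days. The patient must still pass the eligibility limits on hematologic stability, liver tests, creatinine, ejection fraction and systemic disease. The SAE must still be open at first dose, must worsen on drug, and must be kept under its old start date. No text says the AE page handles it that way: the follow-up rule in Protocol 8.1 concerns SAE reporting and does not set start dates on the AE page. This stands as a limit on size. It does not remove the mismatch, because the SAP does not say how such a record is dated either.

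A reader might infer more: that any pre-dose condition worsening on drug disappears from every AE table. The documents do not support that. Non-serious pre-dose events sit on the Medical History page and their worsening is a new AE, and the outputs listed at the end of Step 4 do not depend on the rule.

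A reader might also link the gap to Protocol 1.3, which places cytopenias, hepatic failure and raised transaminases mostly in patients with existing disease, and conclude that these harms are hidden. Those are chronic baseline conditions, not open screening SAEs. Their deterioration should enter as new AEs and is also seen in the laboratory tables whatever the AE dates.

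**Conclusion.** Wrong as written, minor severity. SAP 2.8.1 narrows the protocol's definition and Section 4 does not declare it. The loss is confined to AE-page records that keep a pre-dose start date and worsen on treatment, chiefly screening SAEs, and to the treatment-emergent frequency tables.

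The number of patients cannot be derived from the documents and is probably small. A percentage undercount would need an assumed number of screening SAEs and an assumed event count, and the documents support neither. Within each arm the error can only lower counts. Its effect on the comparison depends on which arm has more worsening, which is not known in advance.

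The conclusion assumes that at least some sites record worsening on the existing entry. If every site opened a new record dated at the worsening, the two definitions would give the same tables.

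**What to change.** In SAP 2.8.1, restore the protocol definition: a treatment-emergent AE is one that starts or worsens from the first dose to 28 days after the last dose. Add how worsening is found: before unblinding, review AE records with a pre-dose start date that continue past first dose, and date each qualifying event at the worsening. For the registry tables, where records of the same term separated by no more than one day are merged, state which start date the merged event takes.

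Seriousness should not be used as the marker. It is not part of the protocol's definition, and the records mainly affected are already serious.

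If the sponsor prefers the start-date rule, it should be declared and justified in SAP Section 4.

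The cost is a short text change and a small amount of extra data review. The review is needed because the severity field may not show when severity changed, so programming alone may not find these events.
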